6.2.5. Study Exposure

Study vaccine administration data will be presented in a listing.

6.2.6. Major Protocol Deviations

Major protocol deviations are a subset of protocol deviations that may significantly impact the completeness, accuracy, or reliability of the study data or that may significantly affect a subject's rights, safety, or well-being. Major protocol deviations rules will be developed and finalized before database lock.

The number and percentage of the subjects with each major protocol deviation type will be provided by CMV serostatus (CMV-seropositive, CMV-seronegative, and overall) and treatment group as defined in [Section 6.1](#) based on the Randomized Set.

Major protocol deviations will be presented in a listing.

6.2.7. COVID-19 Impact

A listing of COVID-19 impact will be provided.

6.3. Safety Analysis

Safety and reactogenicity assessments will include monitoring and recording of solicited (local and systemic reactogenicity events) ARs and unsolicited AEs, medically-attended AEs, SAEs, AEs leading to discontinuation from study vaccine or participation in the study, clinical laboratory test results including hematology, serum chemistry, and coagulation; vital sign measurements; and physical examination findings. The Toxicity Grading Scale for Healthy Adult and Adolescent Volunteers Enrolled in Preventive Vaccine Clinical Trials [[DHHS 2007](#)] will be used with modification for rash.

All safety analyses will be based on the Safety Set, except summaries of solicited ARs which will be based on the Solicited Safety Set. All safety analyses will be provided by CMV serostatus (CMV-seropositive, CMV-seronegative and overall) and vaccination group, unless otherwise specified.

6.3.1. Adverse Events

An AE is defined as any untoward medical occurrence in a subject or clinical investigation subject who is administered a pharmaceutical product at any dose that does not necessarily have to have a causal relationship with the treatment.

A treatment-emergent AE (TEAE) is defined as any event not present before exposure to study vaccine or any event already present that worsens in intensity or frequency after exposure. Adverse events will also be evaluated by the investigator for the coexistence of medically-attended AE which is defined as an AE that leads to an unscheduled visit to a healthcare practitioner.

Unsolicited adverse events will be coded by PT and SOC using MedDRA and summarized by CMV serostatus (CMV-seropositive, CMV-seronegative and overall), vaccination group and stage (Vaccination Stage, Follow-up Stage, Overall Stage, and 28 days after each vaccination stage [including an overall summary, i.e., after any vaccination]; see [Section 6.1](#) for definitions of vaccination group and stage).

All summary tables (except for the overall summary of AEs) for unsolicited AEs will present SOC and PT, will include counts of subjects, and will be based on TEAEs. SOC will be displayed in internationally agreed order. PT will be displayed in descending order of frequency of total mRNA-1647 and then alphabetically within SOC.

Percentages will be based upon the number of subjects in the Safety Set within each vaccination group.

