#### **3.2. Endpoints**

##### **3.2.1. Primary Endpoints**

- Solicited local and systemic ARs through 7 days after each vaccination.
- Unsolicited AEs through 28 days after each vaccination.
- Medically-attended adverse events (MAAEs) through 6 months after the last vaccination, and serious adverse events (SAEs) throughout the entire study period.

- Geometric mean titer (GMT) of serum neutralizing anti-CMV antibodies against epithelial cell infection and against fibroblast infection, and associated geometric mean ratio (GMR) of post-baseline/baseline titers at each timepoint.
- Proportion of participants with  $\geq 2$ -fold, 3-fold, and 4-fold increases in nAb over baseline against epithelial cell infection and against fibroblast infection at each timepoint.

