5.3. Safety Set

The Safety Set consists of all randomized participants who received any study vaccination. The Safety Set will be used for analysis of safety except for the solicited ARs.

Subjects will be analyzed according to the vaccination group a subject received, rather than the vaccination group to which the subject is randomized to. Subjects who receive a vaccination/injection that is different from the vaccination/injection which the subject is randomized to will be summarized under the highest dose of vaccination group (i.e., mRNA-1647 **CCI** > mRNA-1647 **CCI** > mRNA-1647 **CCI** > Placebo).

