6.1. General Considerations

The Schedule of Assessments is provided in the protocol Table 1 for subjects completing all vaccinations, Table 6 for subjects completing the first 2 vaccinations only, and Table 7 for subjects who completing the first vaccination only.

Continuous variables will be summarized using the following descriptive summary statistics: the number of subjects (n), mean, standard deviation (SD), median, minimum (min), and maximum (max).

Categorical variables will be summarized using counts and percentages.

Baseline value, unless specified otherwise, will be defined as the most recent non-missing measurement (scheduled or unscheduled) collected before the first dose of study vaccination.

For the summary statistics of all numerical variables unless otherwise specified, the display precision will follow programming standards. Please see [Appendix A](#) for variable display standards.

When count data are presented, the percentage will be suppressed when the count is zero in order to draw attention to the non-zero counts. A row denoted “Missing” will be included in count tabulations where specified on the shells to account for dropouts and missing values. The denominator for all percentages will be the number of subjects in that vaccination group within the analysis set of interest, unless otherwise specified.

Study day relative to the first vaccination will be calculated as below:

- a) study day prior to the first vaccination will be calculated as: date of assessment/event – date of the first vaccination;
- b) study day on or after the date of the first vaccination will be calculated as: date of assessment/event – date of the first vaccination + 1;

Study day relative to the most recent vaccination will be calculated as below:

- a) study day prior to the first vaccination will be calculated as: date of assessment/event – date of the first vaccination;
- b) study day on or after the date of the first vaccination but before the second vaccination (if applicable) will be calculated as: date of assessment/event – date of the first vaccination + 1;

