For assessments that will be collected at study visits (eg. laboratory and vital sign), if a subject receives three vaccinations, this stage starts at the first vaccination on Day 1 and continues through the earliest date of (Month 7 visit, withdraw from study, or death); If a subject receives first two vaccinations, this stage starts at the first vaccination on Day 1 and continues through the earliest date of (Month 3 visit, withdraw from study, or death); If a subject receives first vaccination only, this stage starts at the first vaccination on Day 1 and continues through the earliest date of (Month 1 visit, withdraw from study, or death).

- Follow up stage: For assessments that will be collected throughout the study (eg, unsolicited AE), this stage starts at 29 days after the last vaccination (ie, the day of last vaccination and 28 subsequent days, regardless of number of vaccinations received) and continue until the earliest date of (study completion, discontinuation from the study, or death).

There is no planned follow up stage for assessments that will be collected at study visits (eg. laboratory and vital sign).

- Overall stage: This stage starts at the first vaccination on Day 1 and continues through the earliest date of (study completion, discontinuation from the study, or death).
- 28 days after each vaccination stage: This stage starts at the day of each vaccination and continue through the earliest date of (the day of each vaccination and 27 subsequent days, next vaccination (if applicable)).

Unscheduled visits: Unscheduled visit measurements will be included in analysis as follows:

- In scheduled visit windows per specified visit windowing rules.
- In the derivation of baseline/last on-treatment measurements.
- In the derivation of maximum/minimum on-treatment values and maximum/minimum change from baseline values for safety analyses.
- In individual subject data listings as appropriate.

Visit windowing rules: The analysis visit windows for protocol-defined visits are provided in [Appendix B](#).

Incomplete/missing data:

- Imputation rules for missing prior/concomitant medications, non-study vaccinations and procedures are provided in [Appendix C](#).
- Imputation rules for missing AE dates are provided in [Appendix D](#).

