- For laboratory assessments, if majority of results are indefinite, imputation of these values will be considered. If the laboratory results are reported as below the LLOQ (eg, < 0.1), the numeric values will be imputed by $0.5 \times \text{LLOQ}$ in the summary. If the laboratory results are reported as greater than the ULOQ (eg, > 3000), the numeric values will be imputed by ULOQ in the summary.

Other incomplete/missing data will not be imputed, unless specified otherwise.

The following **vaccination groups** will be used for summary purposes:

- mRNA-1647 vaccine: **CCI**

- mRNA-1647 vaccine: CCI
- mRNA-1647 vaccine: CCI
- mRNA-1647 vaccine: Total
- Placebo

Summary by study part and CMV serostatus:

All analyses and data summaries/displays will be provided by CMV serostatus (CMV-seropositive and CMV-seronegative) unless otherwise specified. Analyses and data summaries/displays may be provided by study part (Part 1, Part 2, and/or overall) when specified, please also refer to [Section 6.5 Planned Analyses](#).

For those subjects who were CMV seronegative at Screening and became CMV seropositive at Baseline (before or on the day of 1st vaccination), the subjects will be:

- included in the Randomized Set under the CMV status group the subjects were randomized under, ie, CMV seronegative
- included in the Solicited Safety Set and Safety Set, under CMV seropositive group
- included in the FAS, under CMV seropositive group
- excluded from the PP Set for Antibody-Mediated Immunogenicity data and CMI data

All analyses will be conducted using SAS Version 9.4 or higher.

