6.3.2. Solicited Adverse Reactions

The term “Solicited Adverse Reactions” refers to selected signs and symptoms occurring after vaccination administration during a specified post-vaccination follow-up period (day of vaccination and 6 subsequent days). The solicited ARs are recorded by the subject in eDiary. The occurrence and intensity of selected signs and symptoms is actively solicited from the participant during a specified post-vaccination follow-up period (day of vaccination and 6 subsequent days), using a pre-defined checklist in the eDiary (ie, solicited ARs).

The following local ARs will be solicited: pain at injection site, erythema (redness) at injection site, swelling (hardness) at injection site, and localized axillary swelling or tenderness ipsilateral to the vaccination arm.

The following systemic ARs will be solicited: headache, fatigue, myalgia (muscle aches all over the body), arthralgia (aching in several joints), nausea/vomiting, rash, fever, and chills.

The solicited ARs will be graded based on the grading scales presented in Table 3 in the protocol, modified from the Toxicity Grading Scale for Healthy Adult and Adolescent

Volunteers Enrolled in Preventive Vaccine Clinical Trials ([DHHS 2007](#)). Investigator will assess the Grading for rash and Grade 4 events (with exception of fever). Rash will be graded as:

- Grade 0 = no rash
- Grade 1 = localized without associated symptoms
- Grade 2 = maculopapular rash covering < 50% body surface area
- Grade 3 = urticarial rash covering > 50% body surface area
- Grade 4 = generalized exfoliative, ulcerative or bullous dermatitis

If a solicited local or systemic AR continues beyond 7 days post vaccination, the participant will be prompted to capture solicited local or systemic AR in the eDiary until resolution.

All solicited ARs (local and systemic) will be considered causally related to vaccination.

All solicited ARs analyses will be based on Solicited Safety Set. All solicited ARs analyses will be provided by CMV serostatus (CMV-seropositive, CMV-seronegative and overall) and vaccination group as defined in [Section 6.1](#) for each vaccination (first, second, or third), unless otherwise specified.

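### Unsolicited AE percentages after the second and third vaccination are divided by everyone who received any dose, so they are understated by the share who missed that dose

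*SAP*

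**What the plan says.** Protocol 3.2.1 lists as a primary endpoint "Unsolicited AEs through 28 days after each vaccination". SAP 6.3.1 carries this out by summarizing unsolicited AEs by serostatus and by "vaccination group and stage (Vaccination Stage, Follow-up Stage, Overall Stage, and 28 days after each vaccination stage", with an added summary after any vaccination. The same section then fixes the denominator without distinguishing stages: "Percentages will be based upon the number of subjects in the Safety Set within each vaccination group".

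Three definitions determine what that rule means:

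- **Analysis set.** SAP 5.3: "The Safety Set consists of all randomized participants who received any study vaccination". One dose is enough for membership.
- **Vaccination group.** SAP 6.1 lists the three dose-level arms, "mRNA-1647 vaccine: Total" and placebo. The term describes the assigned product and dose level, not how many doses a person received.
- **Stage.** SAP 6.1: "28 days after each vaccination stage: This stage starts at the day of each vaccination". Someone who did not receive the dose has no such stage.

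The general default in SAP 6.1 points the same way: "The denominator for all percentages will be the number of subjects in that vaccination group within the analysis set of interest, unless otherwise specified". For unsolicited AEs nothing else is specified. For solicited reactions, by contrast, SAP 5.2 defines First, Second and Third Vaccination Solicited Safety Sets, each limited to recipients of that dose who gave diary data. The Safety Set has no counterpart.

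**The concern.** A percentage for the 28 days after dose 3 should answer how often recipients of dose 3 had an event. Under the stated rule the numerator can come only from recipients, while the denominator also holds people who stopped after dose 1 or dose 2, or who skipped dose 2. They are in effect scored as event-free for a dose they never had.

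The protocol expects such people. Section 7.1 covers stopping vaccination early and allows a participant who missed dose 2 to receive dose 3. Tables 6 and 7 give schedules for two-dose and one-dose participants. Section 7.2 says withdrawn participants are not replaced.

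The trial tests no hypotheses, so the descriptive percentages are themselves the safety result. At stake is the AE rate after the later doses of a three-dose schedule, and any comparison of that rate between doses or arms.

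**Working it through.** **The plan's own figure.** The documents give no AE rate and no missed-dose rate. The only computed safety figures are the detection probabilities in SAP 4.2, for an AE with true incidence 2%:

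- Part 1, n = 189: 1 − 0.98^189 = 97.8%; stated as above 95%.
- Part 2, n = 150: 1 − 0.98^150 = 95.2%; stated as above 90%.

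Both reproduce, but neither bears on the denominator.

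**Formula.** For one vaccination group and dose k, let N be its Safety Set size, m the share of N that did not receive dose k, and p the true rate among recipients. Recipients number N(1 − m), and expected participants with an event number pN(1 − m). Dividing by N, as SAP 6.3.1 says, gives

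reported percentage = p(1 − m).

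The relative understatement is exactly m. Dividing by N(1 − m) returns p.

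**Results.** The values of m and p are assumptions, since the documents supply neither.

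| Share missing the dose (m) | True 10% | True 20% | True 30% |
|---|---|---|---|
| 0% | 10.0% | 20.0% | 30.0% |
| 5% | 9.5% | 19.0% | 28.5% |
| 10% | 9.0% | 18.0% | 27.0% |
| 20% | 8.0% | 16.0% | 24.0% |
| 30% | 7.0% | 14.0% | 21.0% |

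**In whole participants.** These use planned Part 1 arm sizes with 3:1 randomization and illustrative counts:

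- Seropositive, per dose level: 0.75 × 24 = 18 on vaccine. If 3 miss dose 3 and 3 of the 15 recipients have an AE, the rate is 3/15 = 20.0%. The table would show 3/18 = 16.7%.
- Seronegative, per dose level: 0.75 × 60 = 45 on vaccine. If 9 miss dose 3 and 7 of the 36 recipients have an AE, the rate is 7/36 = 19.4%. The table would show 7/45 = 15.6%.

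**Unequal losses between arms.** Assume that 20% miss dose 3 on vaccine and 5% on placebo, with a true rate of 20% in both. Vaccine is reported as 0.20 × 0.80 = 16% and placebo as 0.20 × 0.95 = 19%. The apparent ratio is 0.16/0.19 = 0.84 where the true ratio is 1.

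**Which tables are affected.** Only the second- and third-vaccination slices of the 28-day stage. In the regular schedule every Safety Set member has dose 1, so the first-vaccination table has the right denominator. The after-any-vaccination summary and the Vaccination, Follow-up and Overall stages do not depend on receipt of a particular later dose.

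**The case against.** The other side has several fair points.

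- **Size is unknown.** No document gives a missed-dose rate, and the error is zero if nobody misses a dose. This stands; every figure above other than the reproduced ones is conditional on an assumption.
- **Precision is low anyway.** In the 45-person example, 7/36 has an exact 95% interval of about 8% to 36%, and the shift from 19.4% to 15.6% lies well inside it. Protocol Table 5 plans no interval for unsolicited AEs. The pause rules in Protocol 8.9.8 use exposed participants with safety data, so no decision rule depends on these percentages. This lowers the priority. It does not excuse the rule, because the error is systematic and always downward.
- **The right rate can be approximated.** The AE tables carry subject counts, SAP 6.2.1 tabulates receipt of each vaccination, and dosing is listed. This is largely true. However, that disposition table uses the Randomized Set, whereas the Safety Set groups people by vaccine received and moves baseline seroconverters to the seropositive group. The denominators therefore need not match exactly.
- **Table shells may already use a per-dose N.** The shells are not in the documents. The SAP text does not say so.

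Three stronger readings are tempting, and the documents do not support them.

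- A reader might extend the criticism to solicited reactions, because SAP 6.3.2 states "All solicited ARs analyses will be based on Solicited Safety Set". The per-vaccination sets in SAP 5.2 are subsets of that set, require receipt of the dose, and have no evident purpose other than as per-dose denominators. At most a cross-reference is missing.
- A reader might infer that higher-dose arms lose more people and that the rule therefore hides a dose-related difference. AEs are a listed reason for stopping vaccination, so unequal loss is possible, but nothing shows that it occurred.
- A reader might say that the 16% versus 19% example reverses a comparison. Equal true rates have no direction to reverse; the example creates a spurious gap.

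**Conclusion.** The concern holds for the unsolicited AE tables covering the 28 days after the second and after the third vaccination. SAP 6.3.1 states an explicit denominator that gives the wrong quantity for those tables, and no other section makes an exception. The understatement equals, in relative terms, the share of the group that missed the dose. Under assumed shares of 5% to 20%, a true 20% is reported as 19% to 16%; with no missed doses nothing changes. A spurious difference between arms arises only if missed doses also differ by arm, which is a further assumption.

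This should be corrected because it concerns a primary safety endpoint and is simple to put right. It is not a critical flaw: the tables are descriptive, the effect size is unknown, and the published counts would allow an approximate correction.

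**What to change.** In SAP 6.3.1, qualify the denominator sentence. For each table covering the 28 days after the k-th vaccination, use the Safety Set participants in that vaccination group who received the k-th vaccination, and show that N in the column header. Keep the full Safety Set for the after-any-vaccination summary and for the Vaccination, Follow-up and Overall stages. Defining First, Second and Third Vaccination Safety Sets, parallel to SAP 5.2, would do this neatly.

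As an optional clarification only, SAP 6.3.2 could name the existing First, Second and Third Vaccination Solicited Safety Sets as the denominators of its per-vaccination tables.

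The cost is a sentence or two in the SAP and a change of denominator in the programs. No new data are needed. SAP version 5.0 is dated before the final database lock and so leaves room for the change. The corrected percentages would still describe people who went on to the later dose, who may differ from those who stopped; the change removes the dilution, not that selection.

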6.3.1.1. Incidence of Adverse Events

An overall summary of unsolicited TEAEs including the number and percentage of subjects who experience the following will be presented:

- Any unsolicited TEAEs
- Any serious TEAEs
- Any unsolicited TEAEs that are medically-attended
- Any unsolicited TEAEs leading to discontinuation from study vaccine
- Any unsolicited TEAEs leading to discontinuation from participation in the study
- Any unsolicited TEAEs of Grade 3 or higher
- Any unsolicited TEAEs that are fatal
- Any non-serious unsolicited TEAEs
- Any non-serious unsolicited TEAEs Grade 3 or higher

The table will also include number and percentage of subjects with unsolicited TEAEs that are treatment-related in each of the above categories.

In addition, separate listings containing individual subject adverse event data for all unsolicited TEAEs, TEAEs leading to discontinuation from study vaccine, TEAEs leading to discontinuation from participation in the study, serious TEAEs, and medically-attended TEAEs will be provided separately.

6.3.1.2. TEAEs by System Organ Class and Preferred Term

The following summary tables of TEAEs will be provided by MedDRA SOC and PT using frequency counts and percentages (ie, number and percentage of subjects with an event). SOC will be displayed in internationally agreed order. Within SOC, PT will be displayed in descending frequency of total mRNA-1647 and then alphabetically. When summarizing the number and percentage of subjects with an event, subjects with multiple occurrences of the same AE or a continuing AE will be counted once. Only the maximum severity level will be presented in the severity summaries, and the strongest relationship level will be presented in the relationship summaries:

- All unsolicited TEAEs
- All unsolicited TEAEs that are treatment-related
- All serious TEAEs
- All serious TEAEs that are treatment-related
- All unsolicited TEAEs leading to discontinuation from study vaccine
- All unsolicited TEAEs leading to discontinuation from participation in the study
- All unsolicited TEAEs of Grade 3 or higher
- All unsolicited TEAEs of Grade 3 or higher that are treatment-related
- All unsolicited TEAEs that are medically-attended

Summary tables of unsolicited TEAEs will also be provided by SOC, PT, and severity/toxicity grade (ie, Any Grade, Grade 3, Grade 4, Grade 3 or Higher).

In addition, summary tables of selected unsolicited TEAEs of clinical interest as identified by Standardized MedDRA Query (SMQ) will be provided by PT. The following SMQs will be implemented in this study:

- Anaphylactic Reaction (Algorithmic). For this study, when a combination of terms are searched based on the algorithm, the identified terms need to occur within 24 hours of each other based on AE onset date and time (when available) to qualify as a case for this algorithmic SMQ.
- Cardiomyopathy (Narrow).
- Hypersensitivity (Narrow).
- Cardiac Arrhythmias (Narrow).
- Embolic and Thrombotic Events (Narrow).
- Cardiac Failure (Narrow).
- Ischaemic Heart Disease (Narrow).
- Immune-Mediated/Autoimmune Disorders (Narrow).
- Angioedema (Narrow).
- Central Nervous System Haemorrhages and Cerebrovascular Conditions (Narrow; Level 2 Subordinate SMQ under the Level 1 SMQ of Central Nervous System Vascular Disorders).

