#### **8.9.1.3. Solicited Adverse Reaction**

The occurrence and intensity of selected signs and symptoms is actively solicited from the participant during a specified post-vaccination follow-up period (day of vaccination and 6 subsequent days), using a predefined checklist in the eDiary (ie, solicited ARs).

The following local ARs will be solicited: pain at injection site, erythema (redness) at injection site, swelling/induration (hardness) at injection site, and localized axillary swelling or tenderness ipsilateral to the vaccination arm.

The following systemic ARs will be solicited: headache, fatigue, myalgia (muscle aches all over the body), arthralgia (aching in several joints), nausea/vomiting, rash, fever, and chills.

The study site staff will contact the participant within 24 hours of becoming aware of the event if any of the following occurs within 7 days after study vaccination:

- severe (Grade 3) local or systemic ARs,
- presence of any rash, or
- presence of any underarm swelling or tenderness on the same side as the vaccination arm.

The purpose of the contact is to assess the nature of AR, including assessment of potential pause rules. In the event that rash or underarm swelling or tenderness on the same side as the vaccination arm is reported, the participant will be asked to return to the study clinic for assessment by the Investigator.

Grading scales are presented in [Table 3](#), modified from the Toxicity Grading Scale for Healthy Adult and Adolescent Volunteers Enrolled in Preventative Vaccine Clinical Trials ([DHHS 2007](#)).

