Fever (oral)	< 38.0°C < 100.4°F	38.0 – 38.4°C 100.4 – 101.1°F	38.5 – 38.9°C 101.2 – 102.0°F	39.0 – 40.0°C 102.1 – 104.0°F	> 40.0°C > 104.0°F
Rash*	No rash	Localized rash, without associated symptoms	Maculopapular rash, covering < 50% body surface area	Generalized urticarial, covering > 50% body surface area	Generalized exfoliative, ulcerative or bullous dermatitis, eg, Stevens-Johnson syndrome or erythema multiforme

\* Grading for rash and Grade 4 events per Investigator assessment (with exception of fever)

Grade of solicited local and systemic ARs are defined based on CBER guidance ([DHHS 2007](#)).

If a solicited local or systemic AR continues beyond 7 days post vaccination, the participant will be prompted to capture solicited local or systemic AR in the eDiary until resolution. Adverse reactions recorded in eDiaries beyond Day 7 should be reviewed either via phone call or at the following study visit.

All solicited ARs (local and systemic) will be considered causally related to vaccination.

Note: Any solicited AR that meets any of the following criteria must be entered into the participants' source document and also be recorded as an AE on the Adverse Event eCRF:

- Solicited local or systemic AR that results in a visit to a healthcare provider (MAAE)
- Solicited local or systemic AR that leads to the participant withdrawing from the study or the study vaccination (AE leading to withdrawal)
- Solicited local or systemic AR that otherwise meets the definition of an SAE

At the time of consent, the participants must confirm they will be willing to complete an eDiary via an application downloaded to their smartphone or via a device that is provided at the time of enrollment. Prior to enrollment on Day 1, the participant will be instructed to download the eDiary application, or will be provided an eDiary device to record solicited ARs on Day 1.

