#### **8.9.1.4. Medically-attended Adverse Event**

A MAAE is an AE that leads to a visit to a healthcare practitioner (HCP). This would include visits to study clinic for unscheduled assessments (eg, rash assessment, abnormal laboratory follow-up, etc.), and visits to HCPs external to the clinical site (eg, urgent care, primary care physician, etc.).

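### The MAAE tables count only unsolicited events, so solicited reactions that the protocol makes MAAEs are missing from the by-arm tables of a primary endpoint

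*SAP*

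**What the plan says.** Protocol 3.2.1 lists among the primary endpoints "Medically-attended adverse events (MAAEs) through 6 months after the last vaccination", and SAP 3.1 repeats it. Neither limits it to unsolicited events.

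Three protocol rules decide which solicited reactions become MAAEs:

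- **Recall (8.9.1.3).** In the 7 days after a vaccination, when "rash or underarm swelling or tenderness on the same side as the vaccination arm is reported, the participant will be asked to return" to the clinic for the Investigator to assess. There is no grade threshold.
- **Definition (8.9.1.4).** On which visits count as medical attendance: "This would include visits to study clinic for unscheduled assessments (eg, rash assessment, abnormal laboratory follow-up, etc".
- **Recording (8.9.1.3, note after Table 3).** The AE eCRF must also carry a "Solicited local or systemic AR that results in a visit to a healthcare provider (MAAE", and a "Solicited local or systemic AR that leads to the participant withdrawing from the study or the study vaccination (AE leading to withdrawal", as well as any solicited reaction that is serious.

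The SAP's summary table in 6.3.1.1 has the row "Any unsolicited TEAEs that are medically-attended", and 6.3.1.2 has the SOC/PT table "All unsolicited TEAEs that are medically-attended". The discontinuation tables carry the same limit, for example "All unsolicited TEAEs leading to discontinuation from study vaccine". The serious TEAE tables do not. Nor do the listings of medically-attended TEAEs and of TEAEs leading to discontinuation.

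Protocol Table 5 also limits its MAAE row to unsolicited events, but not its row for discontinuation due to an AE. The text of protocol 9.6.2 names MAAEs without a limit.

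**The concern.** The endpoint covers all MAAEs, but the tables that report it leave out one kind of MAAE that the protocol itself creates. A reader of the study report would take the MAAE row as the endpoint and would not see that the count is partial.

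The omitted events are also not a neutral subset. SAP 6.3.2 treats every solicited reaction as causally related to vaccination, and SAP 6.3.1.1 reports the treatment-related subset of each category. Every omitted MAAE would therefore be, by rule, a treatment-related MAAE. The treatment-related MAAE row is the one most exposed to the omission.

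**Working it through.** The plan states no MAAE figure to reproduce. Its only design figures are the chances of seeing at least one AE of 2% incidence. They check out (1 − 0.98^189 = 97.8%; 1 − 0.98^150 = 95.2%) but do not bear on this point.

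**Tracing one case.** A vaccinee enters a Grade 1 rash in the eDiary on day 3 after a dose and is seen at an unscheduled recall visit.

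1. It is an MAAE under protocol 8.9.1.4, and also under the SAP 6.3.1 definition, which turns on an unscheduled visit to a practitioner.
2. It goes on the AE eCRF under the note after Table 3. That note adds a record; it does not relabel the reaction.
3. It is not unsolicited. The Synopsis (Safety Assessments) defines unsolicited AEs as those outside the solicited set, and SAP 6.3.2 defines solicited reactions as the listed symptoms recorded in the eDiary.
4. It therefore fails the filter in both SAP MAAE tables.
5. It appears in the SAP 6.3.2 tables by grade, day, onset and duration, but none of those tables is split by medical attendance. It is identified as an MAAE only in the listing.

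A contrasting case: the same rash reported verbally and not already in the eDiary must be called unsolicited (8.9.1.3, eDiary rule 2). If medically attended, it would enter the MAAE tables. Whether the event is counted then depends on how it was reported, not on what happened.

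**Size.** The documents give only the arm sizes: about 339 on vaccine and 113 on placebo (protocol 2.3). Everything else here is assumed:

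- a = share with rash or underarm swelling after any dose: 5% to 30% on vaccine (aV), 2% to 5% on placebo (aP)
- r = share of those seen at an unscheduled visit: 50% to 100%, the same in both arms. It may be below 100% because some reports can be dealt with at the scheduled visits 7 days after each dose.
- m = share with any other MAAE: 10% to 30%, equal in both arms and independent of the reactions

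MAAE rate in an arm if solicited MAAEs are counted: m + (1 − m)·a·r. If they are not counted: m.

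Shift in the vaccine-minus-placebo difference: (1 − m)·r·(aV − aP).

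Vaccinees whose MAAE status changes: 339·(1 − m)·aV·r.

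| m | aV | aP | r | Shift | Vaccinees |
|---|---|---|---|---|---|
| 0.20 | 0.05 | 0.05 | 0.50 | 0.80 × 0.50 × 0 = 0 | 6.8 |
| 0.20 | 0.05 | 0.02 | 0.50 | 0.80 × 0.50 × 0.03 = 1.2 points | 6.8 |
| 0.20 | 0.15 | 0.03 | 0.75 | 0.80 × 0.75 × 0.12 = 7.2 points | 30.5 |
| 0.20 | 0.30 | 0.05 | 1.00 | 0.80 × 1.00 × 0.25 = 20.0 points | 81.4 |
| 0.10 | 0.30 | 0.02 | 1.00 | 0.90 × 1.00 × 0.28 = 25.2 points | 91.5 |

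The first and last rows are the smallest and largest shifts that these ranges allow.

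**Discontinuation.** SAP 6.2.1 tabulates premature discontinuation of vaccine and of study, with reasons, by serostatus and vaccination group. Protocol 7.1 and 7.2 include AE among those reasons, with no limit to unsolicited events. A solicited reaction that stops vaccination is therefore counted by arm there, but not in the SAP 6.3.1 discontinuation tables. The two counts can disagree, and no table of discontinuations names the reaction.

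**The case against.** The strongest reply is that the SAP follows the protocol: Table 5 is the protocol's own analysis table for safety parameters, and its MAAE row is limited to unsolicited events. That is true, so the SAP cannot be said to depart from the protocol on MAAEs. But Table 5 then conflicts with the primary endpoint, the MAAE definition and the recording note in the same protocol. Agreement with one side of an inconsistency does not resolve it.

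A second reply is that the data are safe. The medically-attended listing is unrestricted, serious TEAEs are tabulated in full, and solicited reactions are tabulated by grade. This stands, and it limits the harm. None of these gives an MAAE rate by arm, though, and grade is no substitute, because a Grade 1 rash triggers the recall.

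A third reply is that leaving out protocol-ordered recalls keeps reactogenicity from inflating the MAAE count. This is a fair reason to show them separately. It does not justify leaving out, under the same filter, a solicited reaction that took the participant to an outside provider.

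Two stronger readings are not supported. A reader might infer that reactions leading to discontinuation are missing from every by-arm table; the disposition table counts them. A reader might also infer that the classification is wholly open, so that two programmers could produce different tables. The definitions mostly settle it, towards exclusion. What is missing is an explicit sentence and a complete count.

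**Conclusion.** The point holds. As written, the plan under-counts MAAEs, a primary safety endpoint: solicited reactions captured in the eDiary that become MAAEs are in no by-arm MAAE table. The SAP should be changed before the final database lock.

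That conclusion rests on the text alone. The size does not follow from the documents. The assumed rates give a shift of 0 to about 25 points, and the effect is trivial at the low end, so no single figure from the table should be quoted as the expected bias. The study tests no hypothesis and plans no confidence interval for MAAEs, so what is at stake is the accuracy of a descriptive safety summary.

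For discontinuation, which is not a primary endpoint, the issue is narrower: the AE tables may not reconcile with disposition.

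**What to change.** Add one paragraph to SAP 6.3.1:

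- Solicited reactions entered on the AE eCRF keep the label solicited.
- The MAAE tables show three rows: unsolicited, solicited, and all. The last row is the one that matches the primary endpoint.
- Where the eCRF allows, protocol-ordered study-clinic recalls are separated from other medical visits.
- The TEAE discontinuation tables gain an all-AE row, to be reconciled with disposition. The disposition table uses the Randomized Set and the AE tables use the Safety Set as treated, so small differences from that source should be footnoted.

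The cost is that paragraph and a few rows in existing tables. The records are already required on the AE eCRF, so no new data or diary coding is needed. The documents do not show whether the eCRF records where a visit took place; if it does not, the recall split is dropped. The downside is that Grade 1 recalls raise the all-MAAE figure, but the separate rows make that visible.
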